It is expected that most patients will receive between 1 and 8 months of treatment with derazantinib capsules. Dose delays and/or reductions will be allowed when derazantinib-related toxicity is observed (see Section 7.3 Dose Modifications). A related toxicity is defined as any toxicity considered related to derazantinib, i.e., definitively, probably, or possibly related, or when the relationship is unknown.

During the treatment period, patients will be evaluated every 2 weeks for the first cycle (Cycle 1 Days 1 and 15), and once every cycle thereafter (Day 1 of each cycle).

Tumor measurements will be done at Screening (within 28 days prior to the first dose of derazantinib), once every 8 weeks (two cycles) from the day of the first dose for the first six cycles and once every 12 weeks (three cycles) thereafter. For patients with PR or CR, the Investigator should perform a confirmation tumor measurement 4 to 5 weeks after the scan showing PR or CR. For patients with PD per Investigator assessment, a central radiology reviewer confirmation should be received prior to the patient's discontinuation from the study treatment if progression is seen on the first or second on-treatment scan. Patients who discontinue study drug for a reason other than radiographic disease progression, withdrawal of consent, death, or loss to follow-up should continue tumor evaluation visits if possible every 8–12 weeks until they start another anti-cancer therapy, experience disease progression, withdraw consent, die, or are lost to follow-up.

Pharmacodynamic assessments will include evaluation of tumor markers (CA19.9, CA125, CEA), biomarkers (FGF19, FGF21, FGF23), and cell-free circulating tumor deoxyribonucleic acid (ctDNA). Blood samples for tumor markers will be collected for all enrolled patients. Blood samples for biomarkers and ctDNA will be collected only from patients enrolled after completion of the interim analysis, and subject to the granting of appropriate regulatory and IRB/IEC approval. These blood samples will be collected on Day 1 of the first cycle, every 8 weeks (two cycles) for the first six cycles, once every 12 weeks (three cycles) thereafter, and at the End of Treatment visit. All collected samples will be evaluated in batches either during or at the end of the study.

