#### 3.3 Study endpoints

# 3.3.1 Primary endpoints

#### Substudy 1

ORR was selected as the primary endpoint of this study. This endpoint is an acceptable surrogate endpoint of clinical benefit in this disease. ORR will be the proportion of patients with confirmed complete responses and partial responses by central radiology review as per RECIST version 1.1.

#### Substudy 2

PFS 3 will be the proportion of patients who have progression-free survival at 3 months from the first date of receiving study drug as assessed by survival status and central radiology review as per RECIST version 1.1.

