#### **3.3.2** Secondary efficacy endpoints

#### Substudy 1 and Substudy 2

- DoR will be calculated from the first date of documented tumor response to disease progression by central radiology review.
- PFS will be calculated from the first date of receiving study drug until radiographic disease progression by central radiology review or death
- OS will be calculated from the first date of receiving study drug until death.
- Changes in HRQOL and symptom response will be evaluated using the EORTC QLQ-C30, QLQ-BIL21, and EQ-5D VAS.

#### Substudy 2

• ORR will be the proportion of patients with confirmed complete responses and partial responses by central radiology review as per RECIST version 1.1.

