PFS will be calculated as the time from first dose of study drug until disease progression as assessed by BICR, or death from any cause, whichever occurs first. Patients who either have no baseline tumor evaluation or have no post-baseline tumor evaluation will be censored at date of first dose. Patients who discontinue treatment due to reasons other than disease progression by BICR or death will be censored in the PFS analyses as the date of their last tumor evaluation prior to EOT. Patients who progress or die after missing  $\geq 2$  consecutive scheduled tumor assessments will be censored at the date of the last tumor evaluation prior to progression or death. Any disease progression as assessed by BICR, or death occurring after end of treatment visit are not taken into account as a PFS event. For missing end of treatment visit date, a +7 day window compared to the maximum of last dose date, last on treatment visit date will be applied to create a tentative end of treatment visit date and a cut-off for death occurring after this date.

The rules for censoring PFS are summarized in the table below:

Situation	Date of progression or consoring	Outcome
No baseline tumor assessments	Date of first dose	Censored
No post-baseline tumor evaluation	Date of first dose	Censored
Documented radiological	Date of radiological assessment of measured	Progressed
progression	lesions up to EOT	
No radiological progression	Date of last radiological assessment of measured	Censored
	lesions up to EOT	
Treatment discontinuation for	Date of last radiological assessment of measured	Censored
reasons other than radiological	lesions up to EOT	
disease progression by BICR or		
death		
Death before first PD assessment	Date of death	Progressed
Death between adequate assessment	Date of death	Progressed
visits		
Death or radiological progression	Date of last radiological assessment of measured	Censored
after more than two missed tumor	lesions prior to progression or death	
assessment or after end of treatment		

Table 2: Censoring scheme for PFS

The hypothesis being tested is:

Null Hypothesis H0: PFS  $3 \le 0.45$  and Alternative Hypothesis HA: PFS 3 > 0.45

Where PFS 3 is the proportion of patients with a PFS > 3 months (i.e. > 91 days).

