## 3.2.7.2 Analyses of Secondary Efficacy Variables

### 3.2.7.2.1 PFS (Substudy 1 and Substudy 2)

PFS as assessed by BICR will be analyzed as detailed in Section 3.2.7.1 for primary efficacy analysis for Substudy 2.

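### The main PFS analysis drops BICR progression and death after the End of Treatment visit, which contradicts the protocol's PFS definition and is not declared in SAP Section 4

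*SAP*

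**What the plan says.** Protocol 3.3.2 gives the endpoint: "PFS will be calculated from the first date of receiving study drug until radiographic disease progression by central radiology review or death". SAP 1.3.2 uses the same words. For Substudy 2, Protocol 3.3.1 builds the primary endpoint on it: "PFS 3 will be the proportion of patients who have progression-free survival at 3 months from the first date of receiving study drug". None of these mentions the End of Treatment (EOT) visit.

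The first sentence of the PFS paragraph in SAP 3.2.7.1 agrees, ending PFS at BICR progression "or death from any cause, whichever occurs first". Two later sentences of that paragraph do not:

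- Patients who stop for reasons other than BICR progression or death "will be censored in the PFS analyses as the date of their last tumor evaluation prior to EOT".
- "Any disease progression as assessed by BICR, or death occurring after end of treatment visit are not taken into account as a PFS event".

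Table 2 follows the later sentences. It dates progression and censoring by scans up to EOT, and its last row censors death or progression occurring after too many missed scans, ending "assessment or after end of treatment". If the EOT date is missing, a cut-off is set 7 days after the later of the last dose and the last on-treatment visit. SAP 3.2.7.2.1 extends all this to the secondary endpoint: "PFS as assessed by BICR will be analyzed as detailed in Section 3.2.7.1 for primary efficacy analysis for Substudy 2".

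Three sensitivity analyses are planned. Table 3 counts stopping without BICR progression as an event, Table 4 counts clinical progression, and Table 5 includes scans after EOT.

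**The concern.** Dropping deaths and central progressions that the definition counts changes what is estimated. The affected patients are also a selected group. Protocol 5.7.1 lets treatment stop for documented clinical progression, and such patients may well progress radiographically or die soon afterwards. Censoring them at an earlier scan treats them as having the same outlook as patients still on treatment.

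PFS is a secondary endpoint in both substudies, and the same derivation feeds PFS3, the Substudy 2 primary endpoint. The protocol plans to collect the discarded information. Section 3.1 asks that patients who stop without radiographic progression go on having scans, where possible, "until they start another anti-cancer therapy, experience disease progression, withdraw consent, die, or are lost to follow-up". Section 5.6 follows survival from the last dose.

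SAP Section 4 records changes to the populations, disease control rate, stable-disease duration and investigator-assessed endpoints. It does not mention the EOT limit.

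**Working it through.** **1. The texts side by side**

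| Place | Progression or death after EOT |
|---|---|
| Protocol 3.3.2; SAP 1.3.2 | Event |
| SAP 3.2.7.1, first PFS sentence | Event |
| SAP 3.2.7.1, later sentences, and Table 2 | Not an event |
| SAP 3.2.7.2.2 (duration of response) | Event; no EOT limit stated |
| SAP Table 3 and Table 5 | No EOT limit |
| SAP Table 4 | EOT limit kept; clinical progression added as an event |
| SAP Section 4 | EOT limit not listed |

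**2. Direction of the Kaplan-Meier effect (illustration)**

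Assume an exponential time to stopping with median 5.7 months (Protocol 1.5.5), with 58.0% of stops for radiological progression (Protocol 1.5.3) and the other 42.0% censored. Nothing is captured at an EOT scan. The hazard after stopping is HR times the on-treatment BICR-progression hazard. PFS at 12 months:

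| HR after stopping | Table 2 | Protocol definition | Difference |
|---|---|---|---|
| 0.5 | 0.428 | 0.482 | -0.054 |
| 1 | 0.428 | 0.429 | -0.001 |
| 2 | 0.428 | 0.359 | +0.069 |
| 4 | 0.428 | 0.295 | +0.133 |

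The sign depends entirely on risk after stopping.

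**3. Size when the stops are clinical progressions (illustration)**

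The clinical share is 20.2/(58.0 + 20.2) = 0.258, from the earlier all-solid-tumor study in Protocol 1.5.3. The median is 5.7 months. Scans fall at weeks 8, 16 and 24, then every 12 weeks. Progression or death follows an uncaptured clinical stop by 20, 45 or 90 days on average. For Table 5, half of the uncaptured stops start new therapy first. PFS at 12 months, ranges over the three delays:

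| BICR progression captured at EOT scan | Table 2 | Protocol definition | Gap | Table 4 | Table 5 |
|---|---|---|---|---|---|
| 0% | 0.359–0.362 | 0.261–0.288 | 0.074–0.099 | 0.253–0.255 | 0.307–0.321 |
| 50% | 0.303–0.304 | 0.258–0.272 | 0.031–0.045 | 0.254–0.255 | 0.280–0.287 |
| 75% | 0.277–0.278 | 0.256–0.263 | 0.015–0.021 | 0.253–0.254 | 0.266–0.270 |

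Table 5 closes about half the gap. With no capture and a 20-day delay, (0.360 - 0.307)/(0.360 - 0.261) = 0.54.

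**4. PFS3**

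The plan's figures come first. The probability of rejection is the sum over x = 8 to 15 of P(Bin(15, p) = x) × P(Bin(28, p) ≥ 25 - x). At p = 0.45 this is 0.0481, and at p = 0.65 it is 0.8035. Both agree with the SAP (0.0481 and about 0.8).

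A patient's Table 2 time is either the protocol-definition time or an earlier censoring time. The rule therefore cannot move anyone above 91 days. It can move a patient below. Someone who stops between the week 8 and week 16 scans with no EOT scan is censored near day 57, even if a later scan or a first event falls after day 91.

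If patients censored by day 91 count as failures among a fixed 43, one success lost in Stage 2 means 26 are needed in effect. Type I error becomes 0.0264 and power 0.7411. With two lost they are 0.0132 and 0.6544. The number lost is unknown.

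The SAP does not state how such patients count. If they were dropped from the denominator, 24/43 = 0.558 could become 24/41 = 0.585, above the 25/43 = 0.581 needed.

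**The case against.** The protocol has no PFS censoring table, and its Section 10 leaves analysis detail to the SAP, so some added rules are legitimate. PFS in this single-arm study is a descriptive Kaplan-Meier summary with no test attached. The sensitivity analyses go a long way: Tables 3 and 5 have no EOT limit, and Table 4 counts clinical progression, so most of any difference would be visible. All of that stands and limits the weight of the point. It does not remove it, because excluding events that the definition counts is more than detail, and none of the three is the main analysis.

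The large gap in step 3 needs an EOT scan that never captures progression. Protocol 5.4.4 and 6.9 call for a scan at EOT when the previous one did not show progression, although 6.9 also makes it optional if one was done within 28 days. No capture is therefore a worst case.

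Four stronger readings are tempting, and the documents do not support them:

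- *Reported PFS is inflated.* This holds only if risk rises after stopping without BICR progression, and the documents give no such data.
- *The Substudy 2 type I error is inflated.* That would follow if patients censored by day 91 were counted as progression-free. SAP 3.2.7.1 requires PFS above 91 days, which a shorter censored time does not meet.
- *The Stage 1 decision is safe because the count can only rise.* SAP 1.4 reports 8 of 14 without saying which rule was used. Table 5's censoring at new therapy could also lower a count.
- *The data for a correction are assured.* SAP 1.1 limits continued scans to patients who have not had an EOT visit, a condition absent from Protocol 3.1 and 6.9.

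**Conclusion.** The rule is wrong as written. It contradicts the endpoint definition in both documents and the opening of its own paragraph, and it is undeclared. This rests on the text alone and is firm.

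Its numerical effect is not firm. Neither sign nor size can be derived from the documents. If clinical-progression stops occur in the earlier study's proportion and 50% to 75% of them have BICR progression captured at the EOT scan, 12-month PFS is overstated by about 1.5 to 4.5 points. The 7 to 10 points apply only with no capture.

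PFS3 is conservative provided patients censored by day 91 count as failures. The ORR test in Substudy 1 is unaffected. This should be fixed, but it does not overturn the study's tests.

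**What to change.** - Make PFS counting BICR progression or death regardless of EOT the main analysis in both substudies and the basis for PFS3, adapting Table 5. Change both EOT-limited sentences in SAP 3.2.7.1 and the matching Table 2 rows. Keep the present rule as a sensitivity analysis.
- State that patients censored by day 91 count as PFS3 failures in the mITT denominator.
- Use one missed-assessment threshold. The text says two or more; the tables say more than two.
- Reconcile the post-treatment scan wording in SAP 1.1 with Protocol 3.1 and 6.9.
- Declare in Section 4 the departures that remain: censoring at new anti-cancer therapy and after missed assessments.
- Re-derive the Stage 1 count of 8 of 14 under the revised rule.

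The cost is SAP wording and one modified derivation. Reported PFS may be less favourable. Scans after EOT are requested only where possible and may be limited by SAP 1.1, so follow-up will be incomplete and the change closes only part of any gap.

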## 3.4 Study duration

The study is estimated to take approximately 4 years from First Patient First Visit to Last Patient Last Follow-up Visit. It is expected that most patients will receive between 1 and 8 months of treatment with derazantinib capsules.

Patients will receive treatment with derazantinib capsules until death, radiographic disease progression, unacceptable toxicity, or until another of the specified criteria is met for stopping therapy (see Section 5.7). Radiographic progressive disease must be confirmed by central radiology review prior to treatment discontinuation if progression is seen on the first or second on-treatment scan.

In Substudy 1, if the locally-documented (e.g., by NGS) *FGFR2* fusion positive status was tested and not confirmed by FISH by the central laboratory designated by the Sponsor after the commencement of study treatment, these patients will be assessed on a case-by-case basis (see Section 5.7.1).

Once a patient is discontinued from the study treatment, he/she and/or their family will be contacted for the long-term survival at least once every 3 months ( $\pm$  2 weeks) until the study has completed or other discontinuation criteria are met (e.g., death, lost to follow-up, or withdrawal of consent for long-term [survival] follow-up).

For patients who demonstrate continued benefit (in Substudy 1 or Substudy 2) from receiving derazantinib at the time of study closure, the Sponsor aims to provide continued individual access to derazantinib, e.g., under a rollover study protocol, or in the context of compassionate use / named-patient access where applicable.

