#### 5.7 Discontinuation from the treatment or study

#### 5.7.1 Patient discontinuation from treatment

Patients will be removed from the study treatment at any time if they meet any of the following criteria:

- Documented radiographic progression of disease
  - Radiographic progression must be confirmed by central radiology prior to treatment discontinuation if progression is seen on the first or second posttreatment scan
  - Patients may remain on study treatment if, in the opinion of the Investigator and with the agreement of the Medical Monitor, they continue to derive benefit from derazantinib

- Central negative or unconfirmed FISH test result for an *FGFR2* fusion in patients enrolled based on a locally-documented *FGFR2* fusion positive
  - If the central FISH test could not be performed for technical reasons and the patient did not experience radiographic progression, the patient may be allowed to continue the study treatment
  - If the central FISH test result is negative for an *FGFR2* fusion, the patient should be discontinued from the study treatment, other than in exceptional cases when, based on ethical considerations and an individual benefit-risk assessment, discontinuation of the patient from the study treatment is considered unacceptable
- Documented clinical progression of disease
- Clinical unacceptable toxicities despite optimal treatment or dose reduction
- Pregnancy (see Section 8.8.2).
- Patient decision to discontinue treatment and study visits
- Withdrawal of consent from treatment and study follow up calls
- Non-compliance with any part of the study, as assessed by the Investigator or Medical Monitor
- Investigator's decision after discussion with the Medical Monitor or designee
- Death

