A Simon's two-stage design will be used, with approximately 15 patients in Stage 1, and an additional 28 patients if the study proceeds to Stage 2.  $H_0$  will be rejected if a PFS 3 is observed in 25 or more of these 43 patients. The type I error rate is 0.0481, and power is approximately 0.8 when the true PFS 3 rate for derazantinib is p1 = 0.65.

Point estimates, exact 2-sided 95% confidence intervals (Clopper-Pearson) and associated p-value will be provided.

PFS will be analyzed using Kaplan-Meier methodology (Kaplan & Meier 1958). The median duration of PFS will be presented along with the standard error and 2-sided 95% CI. If they are calculable, the 25th and 75th percentiles and the 2-sided 95% CIs around the percentiles will be presented. Kaplan-Meier estimates at 3, 6, 9 and 12 months will also be presented. The Kaplan-Meier survival curves will also be presented.

Additional PFS sensitivity analyses which consider alternative censoring methods as outlined in FDA guidelines (FDA 2018, FDA 2015) will be conducted in the same manner, as described above. These will be performed for the Safety/ITT and mITT populations:

- Sensitivity analysis 1 in Table 3 uses a conservative approach by assigning the date of discontinuation, or missed tumor assessment followed by PD or death as an event date.
- Sensitivity analysis 2 in Table 4 includes clinical progression as an event.
- Sensitivity analysis 3 in Table 5 evaluates PFS including post EOT radiological assessments.

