# Table 3: Censoring scheme for PFS - sensitivity analysis 1 (any change considered as progression event)

Situation	Date of progression or censoring	Outcome
No baseline tumor assessments	Date of first dose	Censored
No post-baseline tumor evaluation	Date of first dose	Censored
Documented radiological progression	Date of radiological assessment of	Progressed
between scheduled visits	measured lesions	
No radiological progression	Date of last radiological assessment	Censored
	of measured lesions	
Treatment discontinuation for reasons	Date of discontinuation	Progressed
other than radiological disease progression		
by BICR or death		
Death before first PD assessment	Date of death	Progressed
Death between adequate assessment visits	Date of death	Progressed
Death or radiological progression after	Date of first missed tumor	Progressed
more than two missed tumor assessment	assessment	

Table 4. 4	Concoring	achama far	DEC	concitivity	analyzia 7	(included	alimiaal	nnognogion)
1 abie 4: v	Censoring	scheme for		- sensitivity		uncidaes	Списа	progression
			~			(		

Situation	Date of progression or censoring	Outcome
No baseline tumor assessments	Date of first dose	Censored
No post-baseline tumor evaluation	Date of first dose	Censored
Documented radiological progression	Date of radiological assessment of	Progressed
	measured lesions up to EOT	
No radiological progression, no clinical	Date of radiological assessment of	Censored
progression	measured lesions up to EOT	
Clinical progression	Date of clinical progression	Progressed
Treatment discontinuation for reasons	Date of radiological assessment of	Censored
other than radiological disease progression	measured lesions up to EOT	
by BICR, clinical progression or death		
Death before first PD assessment	Date of death	Progressed
Death between adequate assessment visits	Date of death	Progressed
Death or radiological progression or	Date of last radiological assessment	Censored
clinical progression after more than two	of measured lesions prior to	
missed tumor assessment or after end of	progression or clinical progression	
treatment	or death	

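### PFS sensitivity analysis 1 does not exempt administrative ends of treatment, so study closure or rollover could be scored as progression and late PFS in that one table understated

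*SAP*

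**What the plan says.** SAP section 3.2.7.1 (Substudy 2) defines three alternative censoring schemes for PFS, and section 3.2.7.2.1 carries the PFS analysis over to both substudies. Sensitivity analysis 1 "uses a conservative approach by assigning the date of discontinuation, or missed tumor assessment followed by PD or death as an event date". Table 3 is subtitled "any change considered as progression event". Three of its rows matter here:

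- "Treatment discontinuation for reasons" "other than radiological disease progression" by BICR or death: date of discontinuation, progressed. No reason is exempted.
- "No radiological progression": date of last radiological assessment, censored.
- "No post-baseline tumor evaluation": date of first dose, censored. The row for no baseline assessment does the same.

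The table does not say which row wins when a patient fits more than one.

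The protocol foresees treatment on this study ending for reasons unrelated to the disease. Section 3.4 says that, for patients with continued benefit "from receiving derazantinib at the time of study closure, the Sponsor aims to provide continued individual access to derazantinib", for example through a rollover protocol or compassionate use. Section 5.8 lets the sponsor stop the study for reasons such as poor enrollment or the end of product development. Section 5.7.1 adds a test-driven stop in Substudy 1: after a negative central FISH result, "the patient should be discontinued from the study treatment, other than in exceptional cases when, based on ethical considerations" and an individual benefit-risk assessment, stopping is judged unacceptable.

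**The concern.** A worst-case analysis may reasonably count stops for toxicity, withdrawal or clinical decline as events, because such stops can hide progression. The closing date of a study cannot. A patient in continued benefit whose study treatment ends only because the study ends has the best-controlled disease, and the length of that patient's PFS record depends on the enrollment date. Scoring that stop as progression brings calendar time into the estimate.

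At stake is how the analysis is read. A gap between the main PFS curve and sensitivity analysis 1 would normally suggest that PFS is fragile to stops that may conceal progression. If closure is in the mix, part of the gap only reflects short follow-up of late enrollees. The missing precedence adds a second problem: two programmers could follow Table 3 faithfully and produce different curves.

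**Working it through.** **1. Does Table 3 conflict with itself?** Take a patient with on-study scans, no BICR progression, alive, whose study treatment ends at closure. Read literally, the discontinuation row gives progressed on the stop date, while the no-progression row gives censored at the last scan. In Table 2 (main PFS) the corresponding two rows give the same date and the same outcome, so the overlap is harmless. In Table 3 they give opposite outcomes.

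**2. Stated figures.** The SAP gives no figure for this analysis. The only design figures in the same section are the Simon type I error (0.0481) and power (about 0.8). With continuation at 8 or more of 15 and rejection at 25 or more of 43, the exact binomial gives 0.0481 at a rate of 0.45 and 0.80 at 0.65. They reproduce, and they do not use Table 3.

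**3. Size, if closure is coded as discontinuation.**

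*Inputs.* The median PFS of 5.7 months (fusions) is from Protocol 1.5.5; the landmarks of 3, 6, 9 and 12 months are from SAP 3.2.7.1. Assumed, because the documents do not give them: exponential PFS, uniform accrual over A = 24 or 36 months, closure F = 3, 6 or 12 months after the last patient starts, and no other stops.

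*Formulas.* S(t) = 2^(−t/5.7), so S(3), S(6), S(9), S(12) = 0.694, 0.482, 0.335, 0.232. Potential follow-up is uniform from F to F + A. If closure counts as an event nothing is censored, and the curve becomes S(t) × P(follow-up > t), where P = 1 for t ≤ F and (A + F − t)/A after that. The share still on treatment at closure is 5.7/(A ln 2) × [S(F) − S(F + A)].

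| A | F | Share relabelled | 6 months | 9 months | 12 months |
|---|---|---|---|---|---|
| closure censored | – | – | 0.482 | 0.335 | 0.232 |
| 24 | 3 | 22.5% | 0.482 × 21/24 = 0.422 | 0.335 × 18/24 = 0.251 | 0.232 × 15/24 = 0.145 |
| 24 | 6 | 15.6% | 0.482 | 0.335 × 21/24 = 0.293 | 0.232 × 18/24 = 0.174 |
| 36 | 3 | 15.7% | 0.482 × 33/36 = 0.442 | 0.335 × 30/36 = 0.279 | 0.232 × 27/36 = 0.174 |
| 36 | 6 | 10.9% | 0.482 | 0.335 × 33/36 = 0.307 | 0.232 × 30/36 = 0.194 |
| 24 or 36 | 12 | 7.5% or 5.2% | 0.482 | 0.335 | 0.232 |

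A Kaplan-Meier simulation of the same scenarios (N = 100, 1000 runs each) agrees to within about 0.003. The median falls to about 5.0-5.2 months when F = 3 and is essentially unchanged when F = 6. The 3-month value moves only if F is below 3. With the 6.7-month median of Protocol 1.5.6, which rests on six patients, S(12) = 0.289 and the same factors give 0.18 to 0.24.

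**4. Separating the intended effect.** If 15% of first endings are non-progression stops counted as events by design (an assumption), the simulated 12-month estimate falls from about 0.23 to 0.18 with closure censored. Counting closure as well takes it to 0.11-0.15 across the same four scenarios with F = 3 or 6. The administrative part can therefore be of similar size to the part the analysis is designed to show.

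**The case against.** The strongest reply is that the harmful coding is an inference. A reader might conclude from Table 3 that the SAP scores every non-progression stop, including patients still benefiting at closure, as progression. The documents do not support that as fact. Protocol 5.7.1 does not list closure or rollover among the reasons for stopping treatment. Section 3.4 speaks of continued access, not discontinuation. SAP section 3.2.1 tabulates the primary reason for stopping without naming categories. The no-progression row would suit a patient still on treatment at the data cut. Nor is it every stop, because patients with no baseline or post-baseline evaluation are censored at first dose. All of this stands, and it makes the point conditional.

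Second, the analysis is openly labelled as conservative, and counting non-progression stops is its design. That stands for stops that may hide progression. It does not justify counting a stop that cannot.

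Third, the bound is shown beside the main analysis and sensitivity analyses 2 and 3, none of which makes an administrative stop an event. That limits the harm.

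Fourth, the size depends on assumed accrual and follow-up. Accrual over 36 months within the stated four-year study would leave up to 12 months after the last entry, in which case no reported landmark changes.

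Finally, no figure here covers the FISH-negative stops. Some unconfirmed patients may continue treatment, and those stopped without a post-baseline scan are censored at first dose.

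**Conclusion.** The point holds in a conditional and limited form. Table 3 has no exception for administrative ends of treatment, and two of its rows give opposite outcomes for the same patient with no rule to choose between them. If closure, sponsor termination or transfer to post-study access is handled as discontinuation, late PFS in sensitivity analysis 1 is understated. Under the assumptions above, 12-month PFS falls from about 0.23 to 0.15-0.19 when closure comes 3 to 6 months after the last patient starts. Nothing changes through month 12 when every patient has at least 12 months of potential follow-up. The documents give no count of patients on treatment at closure, so these figures are illustrations and not estimates for this trial.

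The main PFS analysis, sensitivity analyses 2 and 3, and the Simon decision are untouched. It would be wrong to infer that the trial's conclusions are at risk or that a worst-case analysis is itself a mistake. The point is minor, but worth correcting because the correction is small and removes a real ambiguity.

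**What to change.** In SAP Table 3:

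1. Except from the discontinuation row those patients without BICR progression or death whose study treatment ends only because of study closure, sponsor termination, data cut-off or transfer to rollover or other post-study access. Censor them at the last radiological assessment.
2. State precedence: the two first-dose censoring rows apply first, and for all other stops the discontinuation row overrides the no-progression row.
3. Confirm before database lock that the recorded discontinuation reason or date identifies the administrative stops. The documents do not show that a suitable category exists.
4. Report separately how many Substudy 1 events in this analysis come from stops triggered by a negative central FISH result.

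The cost is a few table lines, a check of the reason codes and one count. The downside is that sensitivity analysis 1 becomes slightly less pessimistic. Its worst-case handling of stops that may conceal progression is kept.
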